Applications of dual energy CT for improving staging and monitoring of therapy response in patients with osseous metastases from castrate-resistant prostate cancer

DUKE CANCER INSTITUTE

A National Cancer Institute-designated Comprehensive Cancer Center

Sponsor: PI – Duke Cancer Institute
Funding Source: Society of Abdominal Radiology
Protocol Source: PI - Duke Cancer Institute
Duke IRB#: Pro00078046

Principal Investigator

[name], M.D.
Dept of Radiology
[name]
[name]
[name]
[name]
Fax

[contact]

Co-Principal Investigator(s)

Name, degree
Email address

Sub-Investigator(s)

[name], MD PhD
[contact]
[name], MD, MBA
[contact]

Statistician

[name],
Ph.D.
[contact]

Lead Study Coordinator

Name, degree TBS
Email address

Regulatory Coordinator

[name].
[contact]

Data Manager

Name, degree
Email address

Original version: Date 10/10/2016

Amended version Date
1:

Protocol Title:

Pilot study to assess feasibility of using dual energy CT to improve staging and monitoring of therapy response in patients with osseous metastases from castrate-resistant prostate cancer.

Short Title:

Dual energy CT for improving staging and monitoring of therapy response in patients with castrate-resistant prostate cancer.

Purpose of the Study:

To evaluate the capabilities of dual energy CT as a more precise and accurate tool for staging and monitoring of therapy response in patients with osseous metastases from castrate-resistant prostate cancer.

Our working hypothesis is that, by providing quantitative material-specific information of tissue composition, dual energy CT may yield more accurate and precise quantitative information for the staging and monitoring of therapy response in patients with osseous metastases from castrate-resistant prostate cancer. State of the art dual-energy MDCT technology, which is available and routinely utilized at Duke University, relies on simultaneous acquisition of two CT datasets at different energy levels, without increasing patient radiation exposure. The dual energy datasets can be used to calculate conventional CT images, similar to a routine single energy CT acquisition, or they can be further processed to extract material-specific information. The latter datasets have proven to be beneficial in multiple clinical scenarios (2-4).

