Patients with osseous metastases from prostate cancer provide a common clinical and diagnostic challenge. Not uncommonly, subclinical metastatic lesions may only become detectable at imaging in response to therapy due to increased bone deposition during the first three months of post therapy. Commonly used imaging tests (such as CT or bone scan) are unable to reliably differentiate this phenomenon (also referred to as “flare”) from progressive metastatic osseous disease. This diagnostic challenge may have profound negative effects on patient management as it will require multiple additional imaging follow-up studies before an accurate assessment of tumor response can be formulated with appropriate management (Prostate Cancer Clinical Trials Working Group 3 [PCWG3]).

We postulate that dual energy CT may provide additional critical information in this clinical scenario. Specifically, by providing material-specific quantitative information on iodine concentration within tissues, dual energy CT may be able to distinguish between iodine uptake within viable metastatic osseous disease and lack of thereof within treatment-related reactive sclerotic lesions. This differentiation may not be possible using conventional attenuation measurements with single-energy CT due to the challenging anatomical environment within the

vertebral body where sclerotic metastatic tissue coexists with the complex structural anatomy of the fine trabecular bone.

Background & Significance:

Prostate cancer (PCA) is the most frequently diagnosed cancer in North America. It is the fourth most common cause of cancer death overall and the third most common cause of cancer death in men. In this cancer, bone represents a preferential site of metastases, and patients with advanced disease have a very high incidence of bone metastases. Autopsy data from prostate cancer patients indicate an incidence of secondary bone lesions as high as 65–75%, preceded only by multiple myeloma. These bone metastases are typically osteosclerotic (i.e. with increased osteoblastic activity), and likely to produce a significant impact on patients' functional status and quality of life, not only related to pain, but also to the relevant risk of skeletal-related events that can negatively impact physical well-being and activities of daily living.

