For part of this investigation we will use commercially available dual-energy CT postprocessing software (SyngoVia VB10, Siemens Helathcare, Forchheim, Germany). At the same time, we will also be working in collaboration with Siemens Healthcare as part of study Pro00078046. Selected and fully anonymized image datasets in dicom format or raw-projection format will be shared with Siemens scientists for the purpose of developing postprocessing software which will be used in the study. While existing dual-energy CT software can be used to separately analize the pre and postcontrast phases, we will work in collaborations with Siemens to elaborate strategies and potentially dedicated prototype software which will register the image datasets and perform advanced dual-energy CT postprocessing.

All reconstructed CT datasets will be stored on a dedicated and password-protected server in the Department of Radiology. The image reconstruction process will take place within the radiology department on a radiology owned and maintained workstation.

Selection of Subjects:

1. Subject Recruitment and Compensation:

Consent Process:

One hundred and fifty eligible participants will be contacted via mail by their attending oncologist (Dr. [name]) prior to their clinically indicated CT scan. The study coordinator will consent eligible participants according to the inclusion criteria provided in the Design & Procedure section. If necessary, the participants will have no less than 24 hours to consider their participation. Consenting will take place in a private room. The prospective participant may have family or a friend present during the consent process, if they wish. At least an hour will be slotted for the consent process, but we will not prevent the subject from asking questions beyond that time. If the subject wishes to consider the study overnight or longer, an additional appointment will be made for the subject to continue the consent process. From the time of initial contact until the participant completes the study they will have complete freedom to access the coordinator by phone, email or in person. Each patient is given the possibility to refrain from the study after the baseline scan or the first follow up examination without any disadvantage regarding clinical treatment or imaging.

[figure not shown]
There will be no financial compensation for participation to this study.

Subject's Capacity to Give Legally Effective Consent:

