An additional identifiable risk to the subjects is the unlikely but not impossible loss of confidentiality. We have taken all the precaution to minimize this risk. Identifiable PHI will remain with their respective CT exam on a radiology department server and on PACS. HIPAA trained Duke personnel will have access to these exams, and only HIPAA trained Duke personnel will be involved in the study. For each exam, a date, exam protocol type, patient name, and patient ID number will be recorded. Files containing these ID numbers and the dates of the exams will be kept by one of the investigators on a password-protected computer.

4. Costs to the Subject:

There will be no cost to the patients entered in the study.

5. Data Analysis & Statistical Considerations:

All image data will be processed using either commercially available software (SyngoVia VB10) or software prototypes developed for dual-energy CT postprocessing. All study data will be analyzed at Duke University. However, to further develop software prototypes which will be needed for image registration and advanced dual-energy CT postprocessing, we will work in collaboration with Siemens scientists as part of project with duke id Pro00078046. This will require we share with Siemens sample datasets, which will include DICOM image series or raw-projection datasets. In all cases, we will only share fully anonymized data.

To ensure consistency and reproducibility of the data, quantitative measurements of iodine uptake will be performed on a dedicated secondary workstation unit (Core2 x6800; Intel, Santa Clara, Ca) equipped with a previously validated custom Matlab-based software (Matlab, Ver. 2009a, Math-Works, Natick, Ma). Qualitative analysis of post-processed datasets will be performed on an offline workstation equipped with Osirix (Pixmeo SARL, Bernex, Switzerland). Statistical analysis will be performed in collaboration with the department of biomedical statistics. Multi-parametric regression analysis will identify whether dual energy based, calcium corrected iodine maps a valuable biomarker for monitoring and staging of

metastatic bone disease in prostate cancer. For the specific objectives of this study we intend to perform the following analyses.

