To demonstrate the feasibility to monitor metastatic bone disease in castration resistant prostate cancer more accurately than regular single energy CT, single phase dual energy CT and technetium bone scans a quantitative analysis of iodine uptake will be performed. ROC statistics will be calculated to find optimal threshold of this biomarker. Qualitative analysis will be done by multiple readers in blinded fashion to determine sensitivity and specificity for distinction between disease progression at first follow-up three month after initiation of therapy. Findings will be correlated with technetium based bone scans.

To analyze the feasibility to detect bone metastasis at baseline more accurately, unenhanced bone marrow imaging will be calculated and additional dual energy based, calcium corrected iodine maps will be used to determine a threshold for detection of vital bone metastasis in order to calculate color coded bone maps for risk of presence of bone metastases. Qualitative analysis will be done by multiple readers in blinded fashion to determine sensitivity and specificity.

To analyze iodine uptake of soft tissue metastasis more accurately and monitor its change during therapy, a ROI based analysis will be performed for suspect metastatic lesions at three time points to see effects of therapy and to distinguish between partial remission, stable disease and progressive disease. A blinded multi reader assessment of iodine maps will be performed to calculate sensitivity and specificity for qualitative analysis of dual energy based examination compared to single-energy CT.

As an exploratory objective we want to determine whether dual energy CT has prognostic capabilities when assessing bone marrow metastases and soft tissue metastasis in terms of therapy response and overall survival. This exploratory objective will require long term follow up and access to patient data exceeding the time period of the baseline and first two follow up CT examinations. Caplan Mayer curves will be drawn and correlated with findings of bone marrow analysis.

Another exploratory objective is to correlate whether adjusted iodine quantification is a viable biomarker for early detection of lymph node metastases, which are too small to fulfill RECIST criteria of a metastasis at baseline but will become evident on follow up. A ROI analysis will be performed to assess whether adjusted iodine uptake might be a viable biomarker for early detection of lymph node metastases.

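### Iodine thresholds are to be chosen in the only cohort described, with no cut rule or internal validation, so accuracy quoted at an accuracy-maximising cut would be optimistic

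*Combined protocol and SAP*

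**What the plan says.** All of the analysis plan is in section 5, Data Analysis & Statistical Considerations.

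- **Primary aim.** The study is to show that bone disease can be monitored "more accurately than regular single energy CT, single phase dual energy CT and technetium bone scans". For the iodine measurement, "ROC statistics will be calculated to find optimal threshold of this biomarker". The criterion that makes a threshold optimal is not given.
- **Baseline detection.** Calcium-corrected iodine maps "will be used to determine a threshold for detection of vital bone metastasis in order to calculate color coded bone maps". The method for setting this second threshold is not given.
- **Sensitivity and specificity.** In the primary paragraph these are assigned to readers: "Qualitative analysis will be done by multiple readers in blinded fashion to determine sensitivity and specificity for distinction between disease progression". The baseline paragraph also ends with blinded readers. No paragraph promises sensitivity or specificity at a threshold.
- **Validation.** The one item described as validated is the measurement tool, a workstation "equipped with a previously validated custom Matlab-based software". No pre-specified cut-off, hold-out sample, cross-validation, bootstrap correction or confirmation cohort appears anywhere.
- **Size and status.** The only number is in the consent text: "One hundred and fifty eligible participants will be contacted via mail". The protocol title calls the work a "Pilot study to assess feasibility of using dual energy CT to improve staging and monitoring of therapy response".

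**The concern.** A cut-off picked because it separates this sample best fits the sample's chance features as well as its real signal. Sensitivity and specificity read off at that cut in the same patients are therefore apparent values, and on average they exceed what the same cut would achieve in new patients.

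The stake is interpretation. A threshold is normally published with its sensitivity and specificity, and here the threshold step sits in the same paragraph as the aim to be more accurate than three comparators. Nothing in the plan stops a reader from taking in-sample accuracy as evidence for that aim. The cut rule also needs settling now, because a rule chosen after the data are seen cannot credibly be called pre-specified.

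**Working it through.** The plan states no figure to reproduce: it gives no expected AUC, progression share, analysed number or sample-size calculation. The check is a simulation under stated assumptions.

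**Assumptions (none from the documents except 150, the number contacted).** One independent iodine value per patient, normal with equal variances in progressors and others; higher values indicate disease; true AUC 0.70 or 0.90.

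**Formulas.**
- Separation of the two groups: d = √2 × Φ⁻¹(AUC).
- True values at a cut t: sensitivity = 1 − Φ(t − d), specificity = Φ(t).
- Youden cut: the t that maximises apparent sensitivity + specificity − 1.
- Optimism = apparent value minus true value at the same t, averaged over repeats.

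**One scenario in full** (45 progressors, 105 others, AUC 0.70, 4,000 repeats).
- Mean apparent sensitivity 0.690 against true 0.633, a difference of 5.7 points.
- Mean apparent specificity 0.663 against true 0.638, a difference of 2.4 points before rounding.
- Apparent Youden index 0.690 + 0.663 − 1 = 0.353; true 0.633 + 0.638 − 1 = 0.271. The best attainable with any cut is 2Φ(d/2) − 1 = 0.289, so the apparent value exceeds what even the perfect cut could deliver.

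**Optimism with a Youden cut**, sensitivity / specificity in points (6,000 repeats per cell; repeat runs differ by a few tenths of a point):

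| Progressors / others | AUC 0.70 | AUC 0.90 |
|---|---|---|
| 30 / 120 | 7.7 / 1.9 | 5.5 / 1.4 |
| 45 / 105 | 5.9 / 2.4 | 4.2 / 1.7 |
| 75 / 75 | 3.6 / 3.6 | 2.6 / 2.6 |
| 15 / 45 | 10.9 / 3.7 | 7.9 / 2.6 |
| 10 / 30 | 13.7 / 4.3 | 10.1 / 3.3 |

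At 150 patients the range is thus 2.6 to 7.7 for sensitivity and 1.4 to 3.6 for specificity. At 40 to 60 patients it is 7.9 to 13.7 and 2.6 to 4.3. A marker with no value at all shows a mean apparent Youden index of 0.106 at 45/105 and 0.168 at 15/45.

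**Other cut rules.**
- Closest-to-corner, AUC 0.70, 45/105: 4.0 / 1.8 points.
- Specificity held at 90%, AUC 0.70: 0.4 / 0.6 at 45/105 and 1.6 / 1.3 at 15/45.
- The same rule with the cut placed on an observed value, AUC 0.80: 0.2 / 0.8 with 150 patients and 0.0 / 3.3 with 40. The 3.3 is largely rounding: with 28 non-progressors the cut falls at 26/28 = 0.929 apparent, against 0.896 true.

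**Baseline threshold, if set on lesions.** With five lesions per patient, within-patient correlation 0.6, 20 to 80% of lesions viable, AUC 0.70 and a Youden cut, optimism is 0.7 to 3.3 points with 150 patients, 1.5 to 6.1 with 60 and 1.8 to 8.0 with 40. The larger value falls on the rarer lesion class.

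**Does internal validation help?** Mean Youden index, AUC 0.70:
- Bootstrap optimism correction, 45/105: apparent 0.346, corrected 0.289, true 0.273. It removes 0.346 − 0.289 = 0.057 of the 0.346 − 0.273 = 0.073.
- Ten-fold cross-validation repeated 20 times, 15/45: apparent 0.402, validated 0.257, true 0.263.

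**The case against.** The strongest reply is that no analysis the plan commits to is shown to be biased. ROC is used only to find a threshold, the promised sensitivity and specificity come from blinded readers, and deriving a candidate cut-off is a proper aim for a pilot. All of that stands, and it limits the point to accuracy quoted at the threshold.

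Three stronger readings are tempting and are not supported:

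- *The reader figures are biased by the ROC step.* They would be only if readers score maps built from the threshold or apply it themselves. Map construction and reader accuracy stand in consecutive sentences of the baseline paragraph, but the text does not link them.
- *The comparison leans towards dual-energy CT.* The plan does not describe how the comparators will be analysed, so no direction can be inferred.
- *Any threshold from these data is materially optimistic.* A fixed-specificity rule gives little bias. An accuracy-maximising rule is the natural meaning of an optimal threshold, but the plan does not name one.

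It can also be said that the bias is small beside sampling error: at 45/105 the 5.7 points compare with a standard deviation of 13.6 for apparent sensitivity, a ratio of 5.7/13.6 = 0.42. That is true, but the bias runs in a known direction, and an interval around the apparent value does not absorb it: nominal 95% percentile bootstrap intervals for the apparent Youden index covered the truth in only 51 to 68% of simulations at AUC 0.70.

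Finally, internal validation improves total error only modestly. The root mean squared error of the Youden index falls from 0.173 to 0.148 at 15/45 and from 0.101 to 0.094 at 45/105. For sensitivity alone at 15/45 it rises from 0.141 to 0.154. This stands: the gain is removal of bias, not precision.

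**Conclusion.** The point holds in conditional form. Two thresholds are set in the only cohort described, without a cut rule or internal validation. If the cut maximises accuracy, sensitivity and specificity quoted at it in these patients are optimistic in expectation.

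Under a Youden cut and an assumed AUC of 0.70 to 0.90, the size for one value per patient is about 3 to 8 points in sensitivity and 1 to 4 in specificity if all 150 contacted patients were evaluable. It is about 8 to 14 and 3 to 4 with 40 to 60 patients, a quarter progressing. A fixed-specificity cut would give about 0.5 to 1 point at 150 and 1 to 2 at 40 to 60, apart from the 3.3 points in specificity in the one 40-patient variant above. The AUC does not depend on the cut and is unaffected. A reader might infer that the planned reader accuracy is itself inflated; the documents leave that open and do not support stating it.

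This should be fixed before analysis. It does not call the pilot's design into question.

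**What to change.** In section 5, for both thresholds:

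1. State the direction and the cut rule before analysis. The Purpose section already implies the direction, since it expects iodine to "distinguish between iodine uptake within viable metastatic osseous disease and lack of thereof within treatment-related reactive sclerotic lesions".
2. If sensitivity and specificity at a threshold are reported, take them from internal validation that re-runs the threshold choice each time, by bootstrap optimism correction or cross-validation. Make the patient the resampling unit, with all lesions and scans of a patient kept together. Give apparent values second. The checks above used one value per patient, so the lesion-level version should be tried on simulated data first.
3. Label the threshold developmental, to be confirmed in new patients, and do not use apparent accuracy as evidence of being more accurate than the comparators.
4. State whether readers see threshold-built maps or apply a threshold. If they do, label that reader accuracy developmental too.

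**Cost.** A short analysis script and a few sentences; no new patients, scans or readers. Estimates will be less favourable and somewhat more variable: at 15/45 and AUC 0.70, the standard deviation of the Youden index rises from 0.112 (apparent) to 0.155 (repeated cross-validation). Items 1, 3 and 4 need only wording.

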Castrate-resistant PCA presents a spectrum of disease ranging from rising prostate-specific antigen (PSA) levels in the absence of metastases or symptoms and despite androgen-deprivation therapy, to metastases and significant debilitation from cancer symptoms. Castrate-resistant PCA is usually suspected in patients with new symptoms on androgen deprivation therapy, with a rising PSA, or with new evidence of disease on bone scans or CT scans.

Novel hormonal agents such as abiraterone acetate and enzalutamide improved survival significantly for patients with metastatic castration-resistant prostate cancer. Nevertheless, median survival is limited to 35 months after initiation of therapy. Therefore, it is beneficial to have a more accurate diagnostic measure to assess time to progression, either for patients to receive optimal therapy regimes or for studies to have a more accurate time to progression measure (5, 6). For this reason, the PCWG3 defined criteria for progression of the disease. The most challenging task is the assessment of bone metastases in the early phase of therapy due to common onset of a flare phenomenon. The flare phenomenon refers to the increase in radiotracer uptake at previously diagnosed or new previously undetected lesions soon after initiating therapy. Increased uptake is transient, but variable, lasting between three and six months. It is thought that the increase is a response to bone deposition and repair at treated sites. This increase in signal makes the distinction between progression of bone lesions or increased metastatic spread and successful treatment considerably difficult. In CT scans these lesions would appear osteosclerotic and thus could not be distinguished between therapy response and progression. For this reason, the PCWG3 defined progression as “appearance of at least two new lesions on first post-treatment scan, with at least two additional lesions on the next scan (2+2 rule). If at least two additional new lesions are seen on the next (confirmatory) scan, the date of progression is the date of the first post-treatment scan, when the first two new lesions were documented.” This implicates that progression needs to be dated back and diagnosis of progression is delayed by three months typically.

This highlights the critical need to precisely and accurately determine between flare and progressive disease after onset of therapy.

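### The primary aim is comparative, but only iodine gets an accuracy analysis: no comparator measure, and no attenuation measure, is specified to set against it

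*Combined protocol and SAP*

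**What the plan says.** The aim in the primary-objective paragraph of section 5 is to show that metastatic bone disease can be monitored "more accurately than regular single energy CT, single phase dual energy CT and technetium bone scans". The Primary Objective under Purpose of this study is also comparative, though it is framed as feasibility and names only single-energy CT and bone scan.

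The same paragraph of section 5 then specifies three analyses:

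- For iodine uptake: "ROC statistics will be calculated to find optimal threshold of this biomarker".
- For readers: "Qualitative analysis will be done by multiple readers in blinded fashion to determine sensitivity and specificity for distinction between disease progression at first follow-up". The images to be read are not named.
- For bone scan: "Findings will be correlated with technetium based bone scans".

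Earlier in section 5, the only general statement on reading is "Qualitative analysis of post-processed datasets will be performed on an offline workstation". A reader comparison of dual energy with single-energy CT is written out only for the soft-tissue secondary objective.

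The rationale for iodine is given under Purpose of the Study. On separating viable metastasis from treatment-related sclerosis, it says: "This differentiation may not be possible using conventional attenuation measurements with single-energy CT". Background & Significance makes a similar statement about CT reading: "In CT scans these lesions would appear osteosclerotic and thus could not be distinguished between therapy response and progression".

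**The concern.** A claim that one test is more accurate than another needs the same kind of measure on both, taken on the same lesions or patients and against the same reference. Here one test has a ROC curve and a threshold chosen from it, and the others have no stated counterpart. Three things are at stake.

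First, an iodine AUC on its own cannot show that iodine beats attenuation. If attenuation in the same ROIs separated flare from progression equally well, the planned analysis would not reveal it.

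Second, a sensitivity and specificity pair reflects where the call is set as well as how well the test discriminates. If one modality turns out more sensitive and another more specific, the plan has no rule for saying which is more accurate.

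Third, because no comparison is defined, it could be chosen after the data are seen. Setting the tuned iodine cut against fixed reader calls is one possible choice, and on a combined index it would tend to favour iodine even when discrimination is equal.

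**Working it through.** **Step 1. What each modality in the aim receives at first follow-up.** The plan states no AUC, prevalence, effect size or analysed sample size, so there is no figure of its own to reproduce.

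| Modality | Accuracy measure named in the primary paragraph |
|---|---|
| Dual energy iodine | ROC curve and optimal threshold |
| Single-energy CT | None named; may be among the images read, but this is not stated |
| Single-phase dual energy CT | None named |
| Bone scan | Correlation only |

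The regression mentioned in section 5 lists neither outcome nor covariates, so it does not fill the gap. Attenuation appears in the rationale but in none of the analyses.

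**Step 2. What could go wrong if a tuned cut were set against a fixed call.** These inputs are assumptions, not figures from the documents: an equal-variance binormal model, the same AUC for both tests, and a reader fixed at sensitivity s.

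- Separation: d = √2 × Φ⁻¹(AUC)
- Optimal cut: sensitivity = specificity = Φ(d/2), so Youden J = 2Φ(d/2) − 1
- Reader: specificity = Φ(d − Φ⁻¹(s)), so J = s + specificity − 1

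At AUC 0.80, d = √2 × 0.8416 = 1.190. The optimal cut gives Φ(0.595) = 0.724 for both, and J = 0.448.

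- s = 0.80: specificity Φ(1.190 − 0.842) = 0.636, J = 0.436, difference 0.012
- s = 0.90: specificity Φ(1.190 − 1.282) = 0.464, J = 0.364, difference 0.085
- s = 0.95: specificity Φ(1.190 − 1.645) = 0.325, J = 0.275, difference 0.174

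Difference in J over a range of shared AUC:

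| AUC | J at optimal cut | s = 0.80 | s = 0.90 | s = 0.95 |
|---|---|---|---|---|
| 0.70 | 0.289 | 0.029 | 0.095 | 0.156 |
| 0.75 | 0.367 | 0.022 | 0.095 | 0.172 |
| 0.80 | 0.448 | 0.012 | 0.085 | 0.174 |
| 0.85 | 0.536 | 0.003 | 0.063 | 0.157 |

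The model is symmetric, so a reader fixed at the same values of specificity gives the same differences. On sensitivity alone the mismatch can run the other way: at AUC 0.80 the reader's 0.95 exceeds the tuned cut's 0.724. These figures exclude the separate optimism from choosing the cut in the same data.

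**Step 3. Whether a paired AUC comparison removes the problem.** Paired data were simulated with true AUC 0.80 for both tests, 30 to 150 patients, prevalence 0.2 to 0.5, correlation 0 or 0.5, and 3,000 runs per setting. The mean AUC difference lay between −0.002 and +0.002, and iodine ranked higher in 48% to 52% of runs. The simulation used one observation per patient, so it does not represent several ROIs in one patient.

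**The case against.** A reader might infer that the comparators are to get only reader sensitivity and specificity, and that accuracy will be judged by setting the tuned iodine cut against those calls. The documents do not support this. The reader sentence names no modality, the general statement on qualitative analysis ties it to post-processed datasets, and bone scan is given correlation only. The iodine sentence describes finding a threshold and states no contest. A reader-against-reader comparison is compatible with the text, and the soft-tissue paragraph shows the investigators can specify one. This part of the objection stands, so the figures in step 2 are conditional on a comparison that the plan does not specify.

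The size also depends on where readers set their call, which no document gives. If Background & Significance is taken literally, conventional CT is near chance here and equal AUC is not the relevant case. That limits the figures, but it strengthens the reason to measure attenuation, because the literal claim would then be tested.

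Silence is not exclusion. The regression may include attenuation. Section 6 (Data & Safety Monitoring) refers to qualitative scoring without giving a scale, so graded reading is not ruled out. Single-phase dual energy CT is itself quantitative: Design & Procedures notes that existing software can analyse the two phases separately. All of this is fair, but none of it amounts to a specified comparator analysis.

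Finally, this is a feasibility pilot, progression as quoted in the Background is a binary rule, and paired sensitivity and specificity are a legitimate measure. This lowers the weight of the point without removing it, since the text itself sets an aim of greater accuracy. It is also right that formal graded reads of every modality would add real work; the fix does not ask for them.

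**Conclusion.** The point holds as a gap in specification. The plan sets a comparative accuracy aim for its primary objective but specifies a ROC curve and threshold for iodine alone, leaves the modality read unnamed, gives bone scan only correlation, and defines no comparative measure. The premise about attenuation is untested as the plan stands. This conclusion rests on the text and needs no modelling.

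The possible bias towards iodine is secondary and conditional. For a shared AUC of 0.80 under the equal-variance binormal model, it runs from about 0.01 in Youden index at reader sensitivity 0.80 to 0.17 at 0.95. Over AUC 0.70 to 0.85 and reader sensitivity 0.80 to 0.95, it runs from 0.003 to 0.174. It arises only if a tuned cut is set against fixed calls and judged on a combined index, which the plan does not say will be done.

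**What to change.** Amend the primary-objective paragraph of section 5 in two places.

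1. **Quantitative comparison.** In each ROI where iodine is measured, also record attenuation on the conventional-type image reconstructed from the same acquisition, and the single-phase dual energy iodine value. Make the paired difference in AUC the quantitative accuracy comparison, on the same ROIs and against the same reference standard. Allow for clustering of ROIs within patient, for example by a bootstrap that resamples patients. The protocol already says that conventional-type images can be calculated from the dual energy data.

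2. **Reader comparison.** Name the image sets the readers assess. For those sets, record a graded confidence of progression at first follow-up (for example five points), so that a paired multi-reader AUC can be reported beside sensitivity and specificity. This should be settled before reading starts, because graded scores cannot be recovered reliably from binary calls.

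If bone scan stays at correlation only, the aim should not claim greater accuracy than bone scan on that basis.

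The cost is one or two extra values per ROI, slightly longer reads and a little more analysis, including a multi-reader method. No extra scan, reader or patient is needed.
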